3.2 Intervention/Treatment procedures (by visits)

Go NAPSACC is a suite of online tools designed to help child care programs improve their nutrition and physical activity practices. TA coaches from Child Care Aware in Kentucky will facilitate implementation of the Go NAPSACC program by introducing child care programs to the online tools and providing ongoing support using either a basic or enhanced implementation model. To prepare TA coaches for this role, they will be trained and supported by Go NAPSACC specialists (program experts from the research team).

- TA coaches randomized to Basic Go NAPSACC will participate in 2 hour-and-a-half-long training webinars, complete homework over a 3-week period, and have a 30 minute video conference call check-in meeting with the outreach specialist one month after training is complete. Their training will cover the importance of child care programs in encouraging children's healthy eating and physical activity behaviors, the purpose of Go NAPSACC, Go NAPSACC's 5-step improvement process and the tools available for child care providers ("Provider Tools"), their role in implementation, the tools available for coaches to support implementation ("Consultant Tools"), how to provide support remotely, and how COVID-19 may impact Go NAPSACC best practices. Wave 1 and 2 TA coaches will be refreshed on similar topics over two trainings (1-hour each) administered over a 2-week period. The 1-month check-in meeting is to go over any questions or concerns coaches have with implementing the project.
- TA coaches randomized to Enhanced Go NAPSACC will participate in 4 hour-long training webinar sessions and complete homework over a 3-5-week period. Their training will cover all topics in the Basic training plus their role in enhanced implementation, the purpose of the readiness check and how to administer it, and resources available to provide tailored support throughout implementation based on findings from the readiness check. Wave 1 and 2 TA coaches will be refreshed on these same topics through 2 one-and-a-half hour trainings. During implementation, TA coaches will participate in monthly conference calls hosted by a Go NAPSACC specialist to discuss progress, reflect on experiences, and promote peer learning.

During the first few monthly calls, TA coaches will be further refreshed on training relevant to where they are in the process through a part 3 training. After training, coaches will be asked to evaluate the effectiveness of the training during those calls through online surveys. Further, TA coaches will be provided with 2-3 one-on-one coaching sessions to address any specific questions or challenges encountered.

Basic Go NAPSACC

For centers receiving Basic Go NAPSACC, the director will be invited by their TA coach to register for a Go NAPSACC account. The director will then participate in a 1-hour orientation provided by their TA coach to learn how to use Go NAPSACC's online tools and resources. Once the director is trained, they will be encouraged to complete 2 cycles of Go NAPSACC's 5-step improvement process focusing on child nutrition and physical activity. In each cycle of Go NAPSACC, the director will:

- Evaluate their current nutrition and physical activity practices using the self-assessments in these two modules,
- Choose at least 3 goals per module and create an action plan for each goal using online tools that offer flexible step-by-step guidance,
- Work to implement the action plan and meet their chosen goals drawing from the tip and materials resource library, and
- Log progress and completion of goals.

Each cycle will take about 6 months. At the end of the 12 months, the director will retake the self-assessments on child nutrition and physical activity. Throughout this process, the director will receive brief check-ins from their TA coaches via phone, email, or in-person. TA coaches will be asked to log their implementation activities using the TA Activity Log in their Consultant Tools.

Enhanced Go NAPSACC

For centers receiving Enhanced Go NAPSACC, the director will work with their TA coach to identify an implementation team to support the use of the program and improvements in nutrition and physical activity practices. The team will include a center administrator as well as two staff (at a minimum). Before starting Go NAPSACC, the team will work with their TA coach to conduct an assessment of their center's needs, capacity, and resources. At a minimum this readiness check will be completed by all members of the team, but the team can also extend participation out to all center staff. The readiness check will be completed anonymously and returned to the TA coach for scoring. Summarized results will be presented back to the team by the TA coach and used to identify priority issues for which the team would like extra support from the TA coach as they are working through Go NAPSACC.

Once this readiness check is complete, the team will begin their use of Go NAPSACC. All members of the team will be invited to register for a Go NAPSACC account, linked back to their child care center. The team will then participate in a 1-hour orientation provided by their TA coach to learn how to use Go NAPSACC's online tools and resources. Once the team is trained, they will be encouraged to complete 2 cycles of Go NAPSACC's 5-step improvement process focusing on child nutrition and physical activity. The team will be asked to develop a 12-month plan to guide their Go NAPSACC efforts. In each cycle of Go NAPSACC, the team will:

- Evaluate their current nutrition and physical activity practices using the self-assessments in these two modules.
- Choose at least 3 goals per module and create an action plan for each goal using online tools that offer flexible step-by-step guidance.
- Work to implement the action plan and meet their chosen goals drawing from the tip and materials resource library.
- Log progress and completion of goals.

Each cycle will take about 5-6 months. At the end of the 12 months, the team will retake the self-assessments on child nutrition and physical activity. Throughout this process, the team will receive brief check-ins from their TA coaches via phone, email, or in-person. These check-ins will include tailored

prompts to offer extra guidance and support on prioritized issues identified from the needs assessment. In addition, teams from different centers within the same region will participate in 2-3 one-hour meetings hosted by the TA coach. These meetings will provide opportunities to reflect on their efforts and share lessons learned. TA coaches will be asked to log all of their implementation activities using the TA Activity Log in their Consultant Tools.

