2.1 Study Design

This study will use a two-arm cluster randomized controlled design. The unit of randomization is the TA coach, and child care centers will be subject to the same randomization assignment as their TA coach.

In order to be randomized, TA coaches must complete baseline measures and their associated centers must have all participants recruited and baseline data collection must be complete. Once randomized to either Basic Go NAPSACC or Enhanced Go NAPSACC, TAs and centers will be involved in intervention for 12 months. Then follow-up data will be collected from TAs and centers.

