3 STUDY PROCEDURES

3.1 Screening/Baseline Visit procedures

First, all TA coaches will attend a refresher orientation session where they will be refreshed and updated on the relaunch of the project and their roles as both participants and community partners. They will have the opportunity to ask questions and, if willing, sign an addendum consent form explaining the additions. Consented TA coaches will be asked to fill out demographics, TA CFIR context, and COVID-19 impact surveys online through a confidential Qualtrics link. For TA coaches (wave 1 and wave 2) with already enrolled centers, they will be emailed materials and trained on how to reach out to those centers to let them know that our team is relaunching the study and that the study team will be in touch soon to re-engage and consent them. For wave 3 and 4 TA coaches, at their online orientation they will be trained on how to introduce the research study to child care centers in their community using project-provided center recruitment materials. They will also be instructed to target these efforts toward a randomly selected list of centers (drawn from their current caseload) provided by the project team. They will be responsible for gauging initial interest, and then relaying that information to the research team. All TA coaches were previously trained on human subjects protection using the *CIRTI* curriculum (Anderson EE, *CIRTI: Community Involvement in Research Training*, Center for Clinical and Translational Science. University of Illinois at Chicago, 2011; available

at: <http://www.ccts.uic.edu/content/cirtification>). The CIRTification curriculum is geared towards community partners and designed to increase their knowledge of research principles and methods.

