4.4 Statistical Methods

Primary Aim:

Our primary analyses will test the hypothesis under the intent-to-treat (ITT) principle using Generalized Linear Mixed Models (GLMM) that account for the clustering of child care centers within regions/TA. The primary GLMM will include a random intercept for region (b_0) and fixed effects for the baseline value of the primary outcome (β_1) and the intervention (β_2) to test if the differences in mean changes in primary outcomes is zero, where β_0 is the fixed intercept, and e is error.

$$\text{Change in Primary Outcome}_{12m} = \beta_0 + \beta_1 \text{ Primary Outcome}_{\text{baseline}} + \beta_2 \text{ Intervention} + b_0 + e$$

To further explore the intervention effect, we will examine: 1) baseline covariates relevant to change in EPAO scores; 2) interaction between treatment group and other covariates; and 3) completers only. Baseline demographics and EPAO scores will be compared between centers with and without follow-up measures to inspect for potential bias.

Secondary Aims:

Analysis for secondary aims will use statistical models like those applied for primary analysis. Generalized Linear Mixed Models (GLMM) that account for the clustering of child care centers within regions/TA under the intent to treat principle will be utilized. The primary GLMM will include a random intercept for region and fixed effects for the baseline value of the outcome and the intervention. Interaction terms will be added to models where needed. Specifics relevant to aims 2-5 include:

Aim 2. Data used to evaluate adoption, implementation, and maintenance of Basic vs. Enhanced Go NAPSACC will be compiled from the Go NAPSACC registration reports and activity reports (Center and TA). Outcomes computed from these reports include: registration, account initiation, first self-assessments, selection of goal, creating action plans, post cycle self-assessment, TA contacts, and TA implementation activities.

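### The primary model has no wave term, although waves 1-2 entered through a relaunch and no stratification by wave is described

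*Combined protocol and SAP*

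**What the plan says.** **Entry.** Section 2.3 has enrollment run over four waves. Under section 3.1, coaches in waves 1 and 2 already have enrolled centers; they tell those centers about the relaunch and that "the study team will be in touch soon to re-engage and consent them". Research staff then confirm continued interest, and directors and teachers receive consent forms and surveys. Coaches in waves 3 and 4 instead approach centers from a randomly selected list drawn from their caseload.

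**Training (section 3.2).** In the Enhanced arm, "TA coaches randomized to Enhanced Go NAPSACC will participate in 4 hour-long training webinar sessions and complete homework over a 3-5-week period", whereas "Wave 1 and 2 TA coaches will be refreshed on these same topics through 2 one-and-a-half hour trainings". In the Basic arm, "TA coaches randomized to Basic Go NAPSACC will participate in 2 hour-and-a-half-long training webinars, complete homework over a 3-week period", whereas "Wave 1 and 2 TA coaches will be refreshed on similar topics over two trainings (1-hour each) administered over a 2-week period".

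**Allocation.** Section 2.1 sets the conditions for randomization: "TA coaches must complete baseline measures and their associated centers must have all participants recruited and baseline data collection must be complete". The synopsis (Study Phases) gives the same order. Neither makes an exception for waves 1-2. Section 6 refers the reader to sections 2.1, 3.1 and 3.2 for randomization; none of them, nor section 2.2, describes stratification by wave.

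**Model (section 4.4 and synopsis).** "The primary GLMM will include a random intercept for region (b_0) and fixed effects for the baseline value of the primary outcome", plus the intervention. Further baseline covariates are to be examined as exploration, and wave is not named among them.

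**The concern.** Wave is a known structural feature of this trial. Centers in waves 1-2 had earlier contact with the study, went through the pandemic interruption and came back by re-engagement; centers in waves 3-4 were recruited fresh. It is reasonable to expect 12-month change in the EPAO-SR score to differ between the two groups. The coach is the unit of randomization and there are few coaches, so without stratification the two arms can by chance hold different shares of relaunched coaches. Part of any wave difference then appears in the arm contrast. Even with good balance, an omitted prognostic factor adds residual variance.

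A second matter is the order of events in waves 1-2. If coaches knew their arm when they contacted their centers again, re-consent and the self-reported baseline score could differ by arm. The documents do not settle this.

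**Working it through.** **1. The plan's sample size.** Inputs from section 4.5: effect 0.6 SD, alpha 0.05 (two-sided), power 80%, ICC 0.001, cluster size 10 to 15.

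N = 4 x ((1.960 + 0.842) / 0.6)^2 = 87.21; multiplied by 1 + (m - 1) x 0.001.

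- m = 10: 87.21 x 1.009 = 87.99 (table: 88.0)
- m = 15: 87.21 x 1.014 = 88.43 (table: 88.4)

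The stated 88 is reproduced. The cluster-size-10 rows are labelled power 0.2 but reproduce only at 80%.

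**2. Stated training hours (section 3.2).**

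| Arm | Waves 1-2 | Later waves | Difference |
|---|---|---|---|
| Basic | 2 x 1 = 2 h | 2 x 1.5 = 3 h | 1 h |
| Enhanced | 2 x 1.5 = 3 h | 4 x 1 = 4 h | 1 h |
| Enhanced minus Basic | 1 h | 1 h | 0 |

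The reduction is the same in both arms. By itself it favors neither; it matters only if waves are unbalanced between arms.

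**3. Size of a possible shift (assumptions).** Shift = difference between arms in the share of waves 1-2 x wave effect.

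- 0.10 x 0.3 = 0.03 SD, which is 0.03 / 0.6 = 5% of the planned effect
- 0.20 x 0.5 = 0.10 SD, which is 0.10 / 0.6 = 17%

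Neither factor comes from the documents. To see whether 10 to 20 points is plausible, take the 27 coaches in the synopsis, split 13/14 without stratification, with h of them in waves 1-2 (assumed 9 to 18). The number x of these in the first arm is hypergeometric, and the difference in shares is x/13 - (h - x)/14. Its SD is 0.185 (h = 9 or 18) to 0.196 (h = 13), so 10 to 20 points is about half to one SD. The chance of a difference of at least 25 points is 10% to 26%. At exactly 25 points, wave effects of 0.2, 0.5 and 0.8 SD would shift the contrast by 0.05, 0.125 and 0.20 SD (8%, 21% and 33% of 0.6).

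**4. Cost of adjusting.** Noncentral t with noncentrality 0.6 / sqrt(4 x DE / N), DE = 1 + (N/K - 1) x 0.001, and df = K - 2 - number of wave terms, for K coaches and N centers. The wave terms are taken to explain no variance.

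| K / N | No wave term | Relaunch indicator (1 df) | Four-level wave (3 df) |
|---|---|---|---|
| 27 / 97 (synopsis, baseline) | 80.9% | 80.8% | 80.5% |
| 26 / 88 (synopsis, follow-up) | 76.9% | 76.8% | 76.4% |
| 8 / 88 (coaches planned in 2.3 and 4.5) | 64.8% | 61.4% | 48.3% |

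If wave explains an assumed 5% to 10% of outcome variance, power at 26 coaches and 88 centers with four-level wave becomes 78.5% to 80.7%, a gain on 76.9%.

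**5. Order of events, side by side.** Section 2.1 and the synopsis put baseline before randomization. In section 3.1 the session before center contact is general: "First, all TA coaches will attend a refresher orientation session where they will be refreshed and updated on the relaunch of the project". Arm-specific refreshers appear only in section 3.2, with no date relative to re-consent or baseline. The Enhanced refresher covers the enhanced coaching role and the readiness check, topics that a coach would normally have met before only after being allocated to that arm.

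**The case against.** **No bias under random allocation.** Omitting a prognostic factor then causes chance imbalance and lost precision, not systematic error. This stands, and the point is limited accordingly.

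**The plan already adjusts.** It includes the baseline score, a random intercept and exploratory covariates, and it collects COVID-19 impact surveys. This stands in part, so it would be too strong to call wave differences uncontrolled. A region intercept may absorb some of them if waves follow regions and both arms occur within a region. An intercept at coach level would treat the wave difference as between-coach noise, because arm is constant within coach. No listed analysis names wave.

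**Training hours.** If waves 1-2 had been trained before the interruption, the refresher adds to that training, and the stated hours do not compare total exposure. This also stands; the hours show that the waves differ, not which received more.

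**A stronger reading.** A reader might infer that waves 1-2 coaches had arm-specific training before their centers were re-consented, so that selection after allocation is established. The documents do not support this. Section 2.1, the synopsis and the order of section 3.1 place allocation after baseline. The verb *refreshed* is used loosely: section 3.1 applies it to all coaches, and section 3.2 applies it again to the early monthly calls without limiting it to a wave. Research staff, not coaches, confirm continued interest. Nor does any section say that waves 1-2 completed an earlier baseline, so a repeated baseline cannot be asserted. What remains is a hint of earlier arm training that section 2.1 does not address.

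**Conclusion.** The point holds as a modest, inexpensive improvement to the analysis. Waves 1-2 differ from waves 3-4 by design, no stratification by wave is described, and the primary model has no wave term. Chance imbalance across a small number of coaches can therefore shift the arm contrast. The size cannot be determined from the documents: 0.03 to 0.10 SD is illustrative and rests entirely on the assumed imbalance and wave effect. If randomization was in fact balanced within wave, only precision is at stake.

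Selection by arm at re-consent is an open question that needs a statement of timing. It is not a finding, and a wave term would not remove it, because different rates of re-consent by arm within a wave would remain.

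**What to change.** 1. In section 4.4 and the synopsis, add a relaunch indicator (waves 1-2 against waves 3-4) as a fixed effect in the primary and secondary models. Four-level wave is a reasonable alternative at the 27 coaches reported, but not if only 8 took part.
2. Add a sensitivity analysis of the primary outcome restricted to waves 3-4.
3. State whether randomization was stratified by wave, and report coaches and centers by wave and arm.
4. Reconcile section 2.1 with sections 3.1 and 3.2: say when waves 1-2 coaches were allocated relative to re-consent and baseline, and whether any earlier allocation was kept. If allocation came first, correct section 2.1 and report by arm how many previously enrolled centers declined to continue.

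The synopsis already gives follow-up counts, so the term should be fixed before outcomes are compared by arm; if they have been compared, label the adjusted analysis as post hoc.

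Cost: SAP wording, using wave membership that the study already holds; one to three between-coach degrees of freedom (80.9% to 80.8% or 80.5% power at 27 coaches); and a smaller sample, of a size the documents do not give, for the sensitivity analysis.

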3.3 Follow- up procedures (by visits)

Measures from Baseline will be repeated following 12 months of Go NAPSACC participation. Data collection will use the same procedures explained in 3.1. The only addition is that process evaluation questions were added to the Qualtrics link, including questions around the delivery of Basic or Enhanced Go NAPSACC and cost-effectiveness.

In addition, trained research staff will complete interviews over Zoom (via link or call-in phone number) for all TA coaches in a group format based on wave and arm assignment. Trained research staff will also complete Zoom interviews with randomly selected center directors from both arms and teachers from the Enhanced Go NAPSACC arm. Interviews will last approximately 1 hour and will be audio recorded and notes will be taken.

3.4 Unscheduled visits

N/A

3.5 Concomitant Medication documentation

N/A

3.6 Rescue medication administration (if applicable)

N/A

3.7 Subject Completion/Withdrawal procedures

Participants may withdraw at anytime. They are asked to inform the study team by phone or email. If the director withdraws they are asked a few follow-up questions to assess reasons for withdrawal. There are no adverse event criteria for individual withdrawal or full study cessation.

3.8 Screen failure procedures

N/A

4 STUDY EVALUATIONS AND MEASUREMENTS

All baseline measurement will be collected through online Qualtrics surveys. Once TA coaches agree to be a part of the study they are emailed a Qualtrics survey link. Surveys include consent, demographics (general personal demographics; 10 questions), COVID impact (impact on job and work with child care centers; 11 questions), modified Consolidated Framework for Implementation Research (CFIR) questions. The CFIR survey for the TA coaches consists of 48 questions and includes questions from CFIR Constructs: Implementation Climate, Readiness for Implementation- Available Resources, Access to Information and Knowledge, Knowledge and Beliefs About the Intervention, and Self-Efficacy.

Similarly, when directors agree to be enrolled into the study they are emailed a consent form, demographics (general personal and center level demographics; (18 items), COVID impact (impact on center; 24 items), and modified CFIR, Qualtrics survey link (80 items).CFIR constructs for directors include: Networks and Communications, Climate, Implementation Climate, Readiness for Implementation- Available Resources, Access to Information and Knowledge, Knowledge and Beliefs About the Intervention, and Self-Efficacy. At this time, they may also upload a month of menus and policy handbooks (to be coded later by research staff). They are also sent a Qualtrics links to the menu and policy section and two days of the Foods and Beverages provided sections of the Environment and Policy Assessment and Observation- Self Report (EPAO-SR).

Finally, when child care center teachers were enrolled into the study they were emailed a consent form, demographics (personal demographics; 9 items), and CFIR (82 items) Qualtrics survey link. CFIR constructs are the same as the directors noted above. Each teacher is also sent one other Qualtrics link to record normal daily activities for one day (each teacher reports about a different day of the week).

After randomization and 12-months of intervention, TA coaches and child care center providers will participate in follow-up measures. Similar to baseline, most follow-up measures were done through online Qualtrics links. At follow-up TAs were emailed a link to fill out a set of surveys. Surveys will include the same CFIR from baseline and some process questions around their experience with Basic or Enhanced Go NAPSACC with their centers. For the center director these measures will include modified center demographics, the same CFIR survey and EPAO-SR questions from baseline, and some process evaluation questions around their experiences with Basic or Enhanced Go NAPSACC and costs. Child care center teachers will fill out the same CFIR and EPAO-SR surveys from baseline and additional process evaluation questions around their experiences with Basic or Enhanced Go NAPSACC. All TAs will be interviewed in a group format and interviews will be approximately 1- 1 ½ hours. They will be audio recorded and notes will be taken. Trained research staff will also complete Zoom interviews with randomly selected center directors and when relevant their implementation team regarding their experience using Go NAPSACC and making improvements to nutrition and physical activity practices. These interviews will last approximately 1 hour and will be audio recorded and notes will be taken.

